8.3. Discontinuation

8.3.1. Early Termination of Patients From the Study

The criteria for early termination of patients from the study include:

- Withdrawal of consent: A patient has the right to withdraw from the study at any time.
- Patient with prior kidney transplant developing AMR (C4d positive renal biopsy) and for whom rituximab is deemed the appropriate therapy: patient must be terminated from the study and receive standard of care therapy.
- Intake of certain prohibited medications as described in [Section 9.7](#).
- Patient who is receiving ALXN1210 as a part of retreatment ([Section 8.3.2.1](#)) chooses to discontinue ALXN1210.
- The Sponsor Medical Monitor or the Investigator deems it is in the best interest of the patient.

If a patient terminates from the study early, the Sponsor and site monitor will be notified and the assessments specified for the Early Termination (ET) visit (as shown in the Schedule of

Assessments, [Section 7.3, Table 3](#)) will be performed as soon as possible. In addition, a follow-up phone call will be performed 8 weeks (56 days) \pm 5 days following the patient's last dose of ALXN1210, to collect concomitant medications, nonpharmacological therapies and procedures, and AEs.

At the time of the termination, if there is an ongoing AE or an unresolved laboratory result that in the opinion of the investigator, is significantly outside of the reference range and clinically significant ([Section 11.4](#)), the Investigator will attempt to provide follow-up until a satisfactory clinical resolution of the laboratory result or AE is achieved.

The reason for early termination will be recorded on the eCRF.

Patients who terminate early from the study will not be replaced.

8.3.2. Discontinuation of ALXN1210 Treatment and Continuation in the Study

Patients who discontinue ALXN1210 treatment will be allowed to continue in the study for the remainder of the visits without receiving ALXN1210 dosing.

Patients should be permanently discontinued from ALXN1210 treatment if any of the following occur during the study:

- Serious infusion reaction (such as bronchospasm with wheezing or requiring ventilator support or symptomatic hypotension, refer to [Appendix C](#)) or serum sickness-like reactions manifesting 1 to 14 days after drug administration;
- Pregnancy or planned pregnancy; or
- The Sponsor Medical Monitor or the Investigator deems it is in the best interest of the patient.

The Investigator should notify the Medical Monitor as soon as possible prior to discontinuing a patient's study treatment and provide the rationale for discontinuing.

If a patient is discontinued from ALXN1210 treatment, but remains in the study, patient should continue attending his or her scheduled protocol visits until Day 1863. During these visits, all assessments except for ALXN1210 administration as described in the Schedule of Assessments ([Table 1](#), [Table 2](#), and [Table 3](#)) should be performed. The PK/PD (1 sample at any time) and ADA samples will be collected as per protocol schedule until about 39 weeks after the last dose of the study drug.

Any patient who discontinues the ALXN1210 treatment but remains in the study and develops abnormal TMA parameter (as specified in [Section 8.3.2.1](#)) before Day 1863, will have the opportunity for retreatment ([Section 8.3.2.1](#)). If the study drug is discontinued again (after retreatment), then the patient will be terminated from the study and ET procedures and follow-up will be performed as described in [Section 8.3.1](#).

The reason for the treatment discontinuation will be recorded on the eCRF.

If a female patient is permanently discontinued from ALXN1210 treatment due to pregnancy, the Investigator will attempt to follow-up until the outcome of the pregnancy ([Section 11.8](#)).

8.3.2.1. Retreatment of Patients who Discontinue ALXN1210 Treatment

A patient who discontinues ALXN1210 treatment, but remains in the study, and develops abnormal TMA parameter (as indicated by criteria No. 1 below) before Day 1863, may be restarted on ALXN1210, if all 3 conditions below are fulfilled:

1. Evidence of TMA, including thrombocytopenia, evidence of hemolysis, or kidney injury based on any one of the following laboratory findings:
 - Platelet count $< 150,000/\mu\text{L}$, or
 - LDH $> 1.5 \times \text{ULN}$ with hemoglobin $\leq \text{LLN}$ for age and gender, or
 - Serum creatinine $\geq \text{ULN}$ in adults (≥ 18 years of age), or $\geq 97.5^{\text{th}}$ percentile for age ([Appendix A](#)) in adolescents (12 to < 18 years of age).

Note: The TMA laboratory parameter must be confirmed on at least one repeated measure. The above laboratory results can be obtained at either the central laboratory (preferable) or the site's local laboratory.

2. The Investigator believes that the patient will potentially benefit from retreatment, initiates a discussion with the Sponsor Medical Monitor, and provides a medically justified rationale. The Investigator and Medical Monitor mutually agree on retreatment, and the decision is documented.
3. The patient agrees to the consent addendum for retreatment.

If the decision to re-treat with ALXN1210 occurs on a scheduled study visit, then dosing may begin on that day.

- Patient will receive a loading dose of ALXN1210 IV based on the weight recorded at the last visit or more recently (2400 mg for patients weighing ≥ 40 to < 60 kg, 2700 mg for patients weighing ≥ 60 to < 100 kg, 3000 mg for patients weighing ≥ 100 kg). All assessments will be performed per the protocol schedule ([Table 2](#) and [Table 3](#)). If start of the retreatment occurs on a visit which does not include PK/PD sample collection, PK/PD samples will be collected predose and at EOI, along with a predose ADA sample.
- Two weeks after the loading dose, the patient will receive a supplemental maintenance dose of ALXN1210 IV at an unscheduled visit, based on the weight at the last visit or more recently (≥ 40 to < 60 kg = 3000 mg; ≥ 60 to < 100 kg = 3300 mg; ≥ 100 kg = 3600 mg). An abbreviated physical examination will be conducted, vital signs will be collected, and the safety card will be reviewed with the patient. Pharmacokinetic/PD samples will be collected predose and at EOI along with a predose ADA sample.
- Six weeks after the supplemental maintenance dose, the patient will return to the site at the scheduled study visit. At this visit, patient will receive maintenance dose of ALXN1210, undergo all assessments per the protocol schedule ([Table 2](#) and [Table 3](#)), and then continue to attend the visits every 8 weeks per the protocol schedule.

If the decision to re-treat with ALXN1210 occurs between scheduled study visits:

- A supplemental loading dose of ALXN1210 may be administered. An abbreviated physical examination will be conducted, vital signs will be collected, and the safety card will be reviewed with the patient. Pharmacokinetic/PD samples will be collected predose and at EOI along with a predose ADA sample.
- The Medical Monitor and the Investigator will determine administration of maintenance dose of ALXN1210 further to facilitate alignment with Schedule of Assessment ([Table 2](#) and [Table 3](#)) as appropriate. The timing of subsequent visits may be modified to accommodate realignment to Schedule of Assessment, these will not be considered deviations to visit windows.

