Chemistry		X	X	X	X	X	X	X	X	X	X	X	X	X
LDH isozymes ^f		X	X	X	X	X	X	X	X	X	X	X	X	X
Hematology and coagulation ^g		X	X	X	X	X	X	X	X	X	X	X	X	X
Urinalysis and urine chemistry		X	X	X	X	X	X	X	X	X	X	X	X	X
PK/PD sampling ^h	X ^h			X ^h				X ^h			X ^h			X ^h
Exploratory APC activity ⁱ		X	X	X	X	X	X	X	X	X	X	X	X	X
Exploratory serum and plasma biomarkers ^j		X	X	X	X	X	X	X	X	X	X	X	X	X
Exploratory urine biomarkers ^k		X	X	X	X	X	X	X	X	X	X	X	X	X
Immunogenicity (ADA) ^l				X ^l				X ^l			X ^l			X ^l
Review safety card ^m		X	X	X	X	X	X	X	X	X	X	X	X	X
Concomitant medications ⁿ	←Monitor continuously→													
Adverse events	←Monitor continuously→													
ALXN1210 administration ^o	X ^o	X	X	X	X	X	X	X	X	X	X	X	X	X

Abbreviations: ADA = antidrug antibody; APC = alternative pathway of complement; aHUS = atypical hemolytic uremic syndrome; BP = blood pressure; eCRF = electronic case report form; EOI = end of infusion; EQ-5D-3L = EuroQol five dimensions 3 level; ET = early termination; FACIT = functional assessment of chronic illness therapy; LDH = lactate dehydrogenase; PD = pharmacodynamics; PK = pharmacokinetics; QoL = quality of life

Note: For patients who terminate the study early, information on the assessments to be conducted on the ET visit day and further follow-up is provided in [Table 3](#).

Patients who discontinue ALXN1210 treatment, but remain in the study without treatment, should continue attending their scheduled protocol visits until Day 1863 ([Section 8.3.2](#)).

For patients who discontinue ALXN1210 treatment, remain in the study, and further receive retreatment should undergo assessments as described in [Section 8.3.2.1](#).

^a Female patients of childbearing potential only; urine or serum pregnancy test at all required time points. A negative pregnancy test result is required prior to administering ALXN1210 at the indicated study visits.

^b FACIT Fatigue version 4 will be used for patients ≥ 18 years of age at Screening. Pediatric FACIT Fatigue will be used for patients < 18 years of age at Screening.

^c On dosing days, patient-reported assessments will be performed prior to dosing.

^d Abbreviated physical examination consists of a body system relevant examination based upon Investigator judgment and patient symptoms. At least 1 body system must be checked for an abbreviated examination.

Table 2: Schedule of Study Visits and Assessments: Extension Period Day 183 to Day 911 (Continued)

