- ^e Vital sign measurements will be taken after the patient has been resting for at least 5 minutes and will include systolic and diastolic BP (millimeters of mercury [mm Hg]), pulse oximetry, heart rate (beats/minute), respiratory rate (breaths/minute), and temperature (degrees Celsius [°C] or degrees Fahrenheit [°F]). On dosing days, vital signs will be taken predose.
- ^f Serum sample for LDH isozyme testing will only be collected at selected sites at any/all timepoints prior to ALXN1210 dosing, dependent on sample testing availability.
- ^g Assessment for safety, as well as the primary and secondary endpoints.
- ^h Serum samples for PK/PD analysis will be collected predose (within 0.5 hours prior to the start of infusion) and EOI (within 0.5 hours after the EOI) on Days 351, 575, 743, and 911; EOI (within 0.5 hours after the EOI) on Day 183. End of infusion samples will be drawn from the patient's opposite, noninfused arm. In order to minimize needle sticks to the patient, the predose sample may be drawn through the venous access created for the dose infusion, prior to administration of the dose. As noted, the postdose sample must be drawn from the opposite, noninfused arm. For patients who discontinue treatment but remain in the study, 1 PK/PD sample at any time will be collected as per protocol schedule until approximately 39 weeks after the last dose of ALXN1210. In case of retreatment, if the patient starts the retreatment on a scheduled visit which does not include PK/PD sample collection, PK/PD samples must be collected predose and at EOI. If a supplemental dose is administered, PK/PD samples will be collected predose and at EOI. All collection times will be recorded in the eCRF.
- ⁱ Collection will be predose on days of dosing and for days without dosing, at any time that visit day. All collection times will be recorded in the eCRF.
- ^j Collection will be predose on days of dosing and for days without dosing, at any time that visit day. All collection times will be recorded in the eCRF.
- ^k Collection will be predose on days of dosing and for days without dosing, at any time that visit day, and combined with urine stabilizing buffer. All collection times will be recorded in the eCRF.

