- ^l A predose serum sample will be collected on Days 351, 575, 743, and Day 911. For patients who discontinue treatment but remain in the study, ADA sample will be collected at any time during the visits until approximately 39 weeks after the last dose of ALXN1210. In case of retreatment, if the patient starts the retreatment on a scheduled visit which does not include ADA sample collection, a predose ADA sample must be collected. If a supplemental dose is administered, a predose ADA sample will be collected. All collection times will be recorded in the eCRF.
- ^m Review the Clinical Trial Participant Safety Information Card with the patient and discuss the importance of carrying the safety card at all times, and the risks ALXN1210 treatment, including the risk of meningococcal infection.
- ⁿ Concomitant medications must be collected at all study visits (and at the 56 [± 5]-day follow-up phone call for patients who terminate the study early) and checked against the prohibited medication listed in [Section 9.7](#).
- ^o Extension Period begins at the start of Day 183 dosing. The dose of ALXN1210 is based on the patient's body weight recorded at the last visit or more recently. For patients who discontinue ALXN1210 treatment, remain in the study, and further receive retreatment, the dosing details are provided in [Section 8.3.2.1](#).

Table 3: Schedule of Study Visits and Assessments: Extension Period Day 967 to Day 1863

Period	Extension Period																
	967	1023	1079	1135	1191	1247	1303	1359	1415	1471	1527	1583	1639	1695	1751	1807	1863/ ET/EOS
Study Day	±7	±7	±7	±7	±7	±7	±7	±7	±7	±7	±7	±7	±7	±7	±7	±7	±7
Window (day)	±7	±7	±7	±7	±7	±7	±7	±7	±7	±7	±7	±7	±7	±7	±7	±7	±7
Weight	X	X	X	X	X	X	X	X	X	X	X	X	X	X	X	X	X
Pregnancy test ^a	X	X	X	X	X	X	X	X	X	X	X	X	X	X	X	X	X
FACIT-Fatigue questionnaire /Pediatric FACIT-Fatigue questionnaire ^{b,c}				X				X				X				X	X
EQ-5D-3L questionnaire ^c				X				X				X				X	X
Physical examination																	X
Abbreviated physical examination ^d	X	X	X	X	X	X	X	X	X	X	X	X	X	X	X	X	X
Assessment of extra-renal signs or symptoms of aHUS				X				X				X				X	X
Vital signs ^e	X	X	X	X	X	X	X	X	X	X	X	X	X	X	X	X	X
Safety 12-Lead ECG ^f																	X
Chemistry	X	X	X	X	X	X	X	X	X	X	X	X	X	X	X	X	X
LDH isozymes ^g	X	X	X	X	X	X	X	X	X	X	X	X	X	X	X	X	X
Hematology and coagulation ^h	X	X	X	X	X	X	X	X	X	X	X	X	X	X	X	X	X
Urinalysis and urine chemistry	X	X	X	X	X	X	X	X	X	X	X	X	X	X	X	X	X
PK/PD sampling ⁱ			X ⁱ			X ⁱ			X ⁱ				X ⁱ			X ⁱ	X ⁱ

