Exploratory APC activity ^j	X	X	X	X	X	X	X	X	X	X	X	X	X	X	X	X	X
Exploratory serum and plasma biomarkers ^k	X	X	X	X	X	X	X	X	X	X	X	X	X	X	X	X	X
Exploratory urine biomarkers ^l	X	X	X	X	X	X	X	X	X	X	X	X	X	X	X	X	X
Immunogenicity (ADA) ^m			X ^m			X ^m			X ^m				X ^m			X ^m	X ^m
Review safety card ⁿ	X	X	X	X	X	X	X	X	X	X	X	X	X	X	X	X	X
Concomitant medications ^o	←Monitor continuously→																
Adverse events	←Monitor continuously→																
ALXN1210 administration ^p	X	X	X	X	X	X	X	X	X	X	X	X	X	X	X	X	X

Abbreviations: ADA = antidrug antibody; APC = alterative pathway of complement; aHUS = atypical hemolytic uremic syndrome; BP = blood pressure; ECG = electrocardiogram; eCRF = electronic case report form; EOI = end of infusion; EOS = end of study; EQ-5D-3L = EuroQol five dimensions 3 level; ET = early termination; FACIT = functional assessment of chronic illness therapy; LDH = lactate dehydrogenase; PD = pharmacodynamics; PK = pharmacokinetics; QoL = quality of life
Note: If a patient terminates from the study early, ET assessments will be conducted as soon as possible. A follow-up phone call will be performed 8 weeks (56 days) ± 5 days following the patient’s last dose of ALXN1210 to collect information on concomitant medications, nonpharmacological therapies and procedures, and adverse events. Patients who discontinue ALXN1210 treatment, but remain in the study without treatment, should continue attending their scheduled protocol visits until Day 1863 (Section 8.3.2). For patients who discontinue ALXN1210 treatment, remain in the study, and further receive retreatment should undergo assessments as described in Section 8.3.2.1.

^a Female patients of childbearing potential only. Serum pregnancy test on the ET visit day only; urine or serum pregnancy test at all other required time points. A negative pregnancy test result is required prior to administering ALXN1210 to female patients of childbearing potential at the indicated study visits.

^b FACIT Fatigue version 4 will be used for patients ≥ 18 years of age at Screening. Pediatric FACIT Fatigue will be used for patients < 18 years of age at Screening.

Table 3: Schedule of Study Visits and Assessments: Extension Period Day 967 to Day 1863 (Continued)

- ^c On dosing days, patient-reported assessments will be performed prior to dosing.

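### No negative pregnancy test is required before the two off-schedule retreatment doses

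*Protocol*

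**What the plan says.** Section 8.3.2.1 describes two routes back onto drug.

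- **Restart at a scheduled visit.** The loading dose is given with all assessments due at that visit. Then: "Two weeks after the loading dose, the patient will receive a supplemental maintenance dose of ALXN1210 IV at an unscheduled visit".
- **Restart between visits.** "A supplemental loading dose of ALXN1210 may be administered", with later maintenance doses timed by the Medical Monitor and the Investigator.

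For the Week 2 maintenance dose and for the between-visit loading dose, the section gives its own list: "An abbreviated physical examination will be conducted, vital signs will be collected, and the safety card will be reviewed with the patient". PK/PD samples before and after the infusion and a predose ADA sample complete it. The notes under Tables 2 and 3 point retreated patients back to this section: "For patients who discontinue ALXN1210 treatment, remain in the study, and further receive retreatment should undergo assessments as described in" section 8.3.2.1.

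The negative-test rule is in the pregnancy footnotes. Table 2 footnote a reads: "A negative pregnancy test result is required prior to administering ALXN1210 at the indicated study visits". Table 3 footnote a is to the same effect: "A negative pregnancy test result is required prior to administering ALXN1210 to female patients of childbearing potential at the indicated study visits".

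**The concern.** At every scheduled dose the protocol makes a negative result a condition of infusion. That includes Day 15, only 14 days after the test on Day 1. At a restart outside the schedule, no text carries that condition over.

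This is a poor place for the gap. The patient has been off drug. Inclusion Criterion 7 and section 9.10 require contraception on treatment and for 8 months after the last dose. Retreatment stays possible until Day 1863, so a patient can be off drug for longer than 8 months and may have stopped contraception before the restart. None of the three retreatment conditions mentions pregnancy. Section 5.1.2.3 states that ALXN1210 has not been studied in pregnant women. What is at stake is fetal exposure to a loading dose of a long-acting antibody in a pregnancy nobody has recognised.

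**Working it through.** **1. Visit spacing (the plan's own figure).** Section 8.3.2.1 gives visits every 8 weeks. The days in Table 2 (183 to 911) and Table 3 (967 to 1863) are 56 days apart in all 30 intervals, so 8 weeks is reproduced. The scheduled-visit route also closes: 14 + 42 = 56 days. A pregnancy test is marked at each of these visits, and under section 8.3.2 it continues while a patient is off drug.

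**2. Age of the last scheduled test at an off-schedule dose.**

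- Between-visit loading dose, nominal days: 1 to 56 − 1 = 55.
- With ±7-day windows at both ends: up to 56 + 7 + 7 − 1 = 69 days. In the Day 183 to 239 interval, where Day 183 has a ±2-day window: up to 56 + 2 + 7 − 1 = 64 days.
- If restart days were spread evenly over 1 to 55 (an assumption): mean (1 + 55)/2 = 28 days.
- Week 2 maintenance dose after a scheduled-visit restart: 14 days.

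**3. Scheduled dosing visits that carry the rule.**

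- Table 1, Days 1, 15, 71 and 127: 4.
- Table 2: (911 − 183)/56 + 1 = 14.
- Table 3: (1863 − 967)/56 + 1 = 17.
- Total: 4 + 14 + 17 = 35 of 35. For the off-schedule dose types it is 0 of 2.

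Day 1863 is marked for dosing, but its PK/PD and ADA samples may be drawn at any time that day. If it is not a dosing visit, the count is 34 of 34.

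**4. Footnotes extended to supplemental doses.**

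| Assessment | Table 2 | Table 3 | Supplemental-dose sentence |
|---|---|---|---|
| PK/PD | h | i | yes, both: "If a supplemental dose is administered, PK/PD samples will be collected predose and at EOI" |
| ADA | l | m | yes, both: "If a supplemental dose is administered, a predose ADA sample will be collected" |
| Pregnancy test | a | a | no, neither |

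That is 4 of 4 for PK/PD and ADA, and 0 of 2 for pregnancy.

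**5. Other text that might close the gap.**

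- Section 11.4 calls for laboratory samples before each administration. It requires no particular result, and its opening sentence ties pregnancy samples to the Schedule of Assessments.
- Section 11.4.1 ties the pregnancy test to the same schedule.
- Section 7.3 leaves tests at unscheduled visits to the Investigator.
- Section 8.3.2 makes pregnancy a reason for permanent discontinuation, which works only once the pregnancy is known.

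**6. Patients affected.** The documents give no number restarted. Every restarted patient receives at least one off-schedule dose by one route or the other. Assume that 30% to 60% of 55 patients are women of childbearing potential, that 5% to 20% of these stop drug and stay in the study, and that 10% to 50% of those restart.

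- Low: 55 × 0.30 × 0.05 × 0.10 = 0.08.
- High: 55 × 0.60 × 0.20 × 0.50 = 3.3.

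**The case against.** The strongest counter-text is section 11.4. It names serum pregnancy among the samples and refers to Appendix D, which lists beta-hCG. Read broadly, its sentence on sampling before each administration means a pregnancy sample is due before supplemental doses too. That reading is open, but it secures only a sample. The infusion may go ahead before the result is back.

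Other points bear on the size of the problem:

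- **Ordinary interval.** After Day 15, tests are 56 days apart even on drug, so a test up to 55 days old is not unusual in itself. This is true, but each of those tests is done at the dosing visit. The relevant comparison is test to dose, and at scheduled doses both fall at the same visit.
- **Timing of restarts.** Restart needs a confirmed TMA laboratory abnormality. Those laboratory tests are drawn at the same visits as the pregnancy test, so many restarts may come early in the interval. The 28-day mean may therefore be too high. The 1 to 55 day range does not depend on it.
- **The two doses differ.** After a scheduled-visit restart, the Week 2 dose follows a required negative test by 14 days. The between-visit loading dose is the main concern.
- **Existing safeguards.** The Investigator and Medical Monitor must agree on each restart, the patient signs a consent addendum, and contraception applies again once treatment resumes. The addendum is not among the documents, so its content is unknown. Nothing in the two documents makes any of these steps detect an unrecognised pregnancy before the restart dose.

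**Conclusion.** The concern holds. A site that follows the protocol as written may give either off-schedule retreatment dose without a negative pregnancy test. For the between-visit loading dose, the last scheduled test is nominally 1 to 55 days old. That range follows from the visit schedule alone, whereas the patient range of 0.1 to 3.3 rests wholly on assumed proportions. Because the PK/PD and ADA footnotes were extended to supplemental doses and the pregnancy footnote was not, this looks like an oversight rather than a choice.

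The consequence is one of patient safety only: rare, but potentially serious for the fetus. No endpoint, analysis set, sample size or efficacy estimate is affected. The change should be made because the harm is avoidable at almost no cost.

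**What to change.** Add one sentence to both off-schedule paragraphs of section 8.3.2.1 and to footnote a of Tables 2 and 3:

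*A negative urine or serum pregnancy test is required before every retreatment or supplemental dose in female patients of childbearing potential.*

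The word *every* also covers later maintenance doses whose timing the Medical Monitor and Investigator set after a between-visit restart. With this change the test is done at the dosing visit, as it is for scheduled doses. The cost is the added sentence and one urine test per dose, at a visit that already takes place and already draws blood for PK/PD and ADA. No statistical section needs to change.
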